**Tyumen Cardiology Research Center, Tomsk National Research Medical Center, Russian
Academy of Science, Tomsk, Russia**

One-year Cardiac Follow-up of COVID-19 Pneumonia (159)
Study Protocol

13/07/2020

Brief Summary: The primary objective of the study is to assess the cardiac status of COVID-19 pneumonia patients during 1 year after discharge.

Although COVID-19 manifests in most cases with respiratory symptoms, cardiovascular abnormalities are common in hospitalized patients. Patients with cardiovascular risk factors or established disease appear to have a worse prognosis. Myocardial dysfunction could represent a direct manifestation of COVID-19. Investigation of the long-term cardiovascular consequences of COVID-19 is needed. Subjects after COVID-19 pneumonia can present myocardial remodeling for a long time after discharge, even in the absence of prior cardiovascular disease.

Keywords: Covid19; Cardiovascular Disease; Echocardiography

Hypothesis: In patients with COVID-19 pneumonia initiates and aggravates the processes of structural and functional remodeling of the myocardium within 1 year after discharge from the hospital.

Primary Outcome Measure:

Echocardiographic assessment of cardiac function. Echocardiographic assessment of global strain parameters at 3 and 12 months after discharge

[Time Frame: up to one year]

Secondary Outcome Measures:

1. MACCE. Major adverse cardiac and cerebrovascular events: cardiac death, myocardial infarction, or stroke at 3 and 12 months after discharge

[Time Frame: up to one year]

2. Quantitative analysis of parenchymal lung damage. Describe the parenchymal lung damage through a quantitative analysis with chest CT at 3 and 12 months after discharge

[Time Frame: up to one year]

3. Functional exercises capacity assessment. Six-min walk test at 3 and 12 months after discharge

[Time Frame: up to one year]

4. Evaluation of renal function. Measure of creatinine clearance at 3 and 12 months after discharge

[Time Frame: up to one year]

5. Evaluation of inflammation. Analysis for C-reactive protein at 3 and 12 months after discharge

[Time Frame: up to one year]

6. Evaluation of coagulation abnormality. Analysis for activated clotting time at 3 and 12 months

[Time Frame: up to one year]

7. Evaluation of quality of life in first year after discharge. Assessment of the Short Form Health Survey (SF36) at 3 and 12 months after discharge

[Time Frame: up to one year]

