The objective of the study is to evaluate the impact of COVID-19 pneumonia on transthoracic echocardiography and other myocardial parameters during 1 year follow-up to monitor cardio-vascular events and predict outcomes.

Population. According to the protocol, the study included men and women ≥ 18 years old with documented COVID-19 pneumonia 3 month \pm 2 week after discharge. The sample size is 380 people (calculation by the Cochran method and Raosoft calculator). The observation period was 12 months \pm 2 weeks. The planned terms of inclusion in the study are the end of December 2020.

Design: The prospective observational study includes men and women ≥ 18 years old who were 3 month \pm 2 week ago discharged after documented COVID-19 pneumonia. Patients were identified from medical information system of local COVID hospital between April and December 2020. The study will be performed in accordance with the International Conference on Harmonization of Good Clinical Practice and the Declaration of Helsinki. The study protocol was approved by the local ethics committee (Approval Number: 159 from 07/23/2020). Every patient is explained the purpose of the study and benefits of participation. If the patient agrees to participate in the study, he signs an informed consent. All patients included have negative results on a swab test at the end of the hospitalization. Exclusion criteria were impossibility to follow up, cancer, tuberculosis. Patients undergo clinical, instrumental and laboratory diagnostics tests during follow-up visits at 3 and 12 month \pm 2 week after discharge, and telephone interview at 6 month after discharge to collect information on health status, outcomes and treatment adjustments.

The study protocol does not provide for a single way for patients managing. If any cardiovascular abnormalities or other disturbances found 3 months after discharge, the therapy carried out.

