At the visit of 3 and 12 months, the patient is interviewed (complaints, data of the epidemiological and medical history), clinical examination, anthropometry, measurement of temperature, heart rate, blood pressure, oxygen saturation, dyspnea, myalgia are performed. Based on the data obtained, the diagnosis is specified (arterial hypertension, coronary artery disease, arrhythmias, obstructive pulmonary disease, asthma, obesity, metabolic syndrome, diabetes mellitus, obliterating atherosclerosis and others); the basic therapy is adjusted. Each patient undergoes electrocardiography, general and biochemical blood tests, microalbuminuria test. Lungs CT, echocardiography with myocardial strain assessment, six-minute walk test, assessment of symptoms of stress, anxiety and depressive disorders (PSS-10 GAD7, PHQ9, respectively) are performed. According to diagnosis, patients are divided into groups. Examination at visits of patients in 12 months after discharge is carried out according to the approved examination plan in groups. During the observation, the incidence of adverse cardio-cerebral events (MACCE) and the prognostic value of the structural and functional parameters of the myocardium and blood vessels will be assessed.

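### Does tying the 12-month examination to group plans, and leaving SF-36 and activated clotting time off the visit list, put the outcome data at risk?

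*Protocol*

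**What the plan says.** The Primary Outcome Measure is global strain on echocardiography at 3 and 12 months after discharge. Secondary outcomes 2 to 7 (quantitative chest CT, six-minute walk, creatinine clearance, C-reactive protein, activated clotting time, SF-36) carry the same two times. None is restricted to a diagnostic group.

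The Design paragraph makes a general statement: "Patients undergo clinical, instrumental and laboratory diagnostics tests during follow-up visits at 3 and 12 month".

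The closing paragraph on visit procedures gives the detail. It opens with both visits, "At the visit of 3 and 12 months, the patient is interviewed", and goes on to clinical examination and vital signs. It continues: "Each patient undergoes electrocardiography, general and biochemical blood tests, microalbuminuria test". It then lists "Lungs CT, echocardiography with myocardial strain assessment, six-minute walk test" and three questionnaires: "assessment of symptoms of stress, anxiety and depressive disorders (PSS-10 GAD7, PHQ9, respectively) are performed". After that come two sentences on grouping: "According to diagnosis, patients are divided into groups", and "Examination at visits of patients in 12 months after discharge is carried out according to the approved examination plan in groups". The content of that examination plan is not reproduced in the protocol.

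**The concern.** Two features of the visit paragraph invite doubt.

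The first is the grouping sentence. It is the only sentence written specifically for the 12-month examination, and it makes that examination depend on a plan by diagnosis. It does not say whether the group plans add to the common tests or replace them. The sentence naming CT, strain echocardiography and the walk test mentions no visit and does not say that it applies to each patient, although the sentence just before it, on ECG and blood tests, does.

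The second is the list itself. SF-36 is missing although three other questionnaires are named, so the omission cannot be put down to a list that leaves questionnaires out. Activated clotting time is not named either, and a coagulation test is not plainly a general or biochemical blood test.

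The stake would be real if the worst reading were true. The hypothesis is that COVID-19 pneumonia "initiates and aggravates the processes of structural and functional remodeling of the myocardium within 1 year after discharge from the hospital", and the primary outcome needs strain at both times. If one diagnostic group had no strain echocardiography at 12 months, the missing data would depend on diagnosis, which is plausibly related to strain, and the change from 3 to 12 months would describe a selected subset. No later analysis plan can recover a scan or questionnaire that was never done.

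**Working it through.** No figure in the protocol bears on this point, so the check is a comparison of the outcome sections with the visit paragraph.

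**Outcome by outcome.** Every outcome below is set at 3 and 12 months in the outcome sections.

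| Outcome | In the visit paragraph |
|---|---|
| Global strain (primary) | Named |
| Chest CT (secondary 2) | Named |
| Six-minute walk (secondary 3) | Named |
| Creatinine clearance (secondary 4) | Not named; plausibly under biochemical blood tests |
| C-reactive protein (secondary 5) | Not named; plausibly under biochemical blood tests |
| Activated clotting time (secondary 6) | Not named; not clearly covered |
| SF-36 (secondary 7) | Not named |

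The count is 3 named + 2 plausibly covered + 1 unclear + 1 absent = 7. MACCE (secondary 1) is an event outcome rather than a test; the visit paragraph says its incidence is assessed during observation.

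**Is the list meant to be complete?** It does not say so. It omits creatinine clearance and C-reactive protein by name, and nobody would infer that these are not collected. The general reference to laboratory tests in the Design paragraph can take in activated clotting time as well. SF-36 is therefore the one clear omission, and secondary outcome 7 itself names the instrument and both times.

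**Does the grouping sentence remove any test?** Its text removes none. Three statements point to common testing at both visits: the outcome sections (both times, no limit by diagnosis), the Design paragraph (tests at both visits) and the opening of the visit paragraph (both visits). On the most natural reading, the outcome tests are common and the group plans deal with what each diagnosis needs. The reading in which group plans replace the outcome tests would go against the protocol's own primary outcome.

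**Can a loss be calculated?** No. The protocol gives a sample size of 380 but no proportion of patients expected to lack a 12-month test under a group plan. Any precision figure would rest on an invented completion rate and would apply equally to ordinary dropout, so it would say nothing about this sentence. The size of a selection bias cannot be derived either.

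**The case for a change.** The strongest case for a change is that deciding which tests are done, in whom and when belongs in a protocol and cannot be left to the analysis. The Design paragraph names no test, so it cannot settle what each group receives at 12 months, and the opening words of the visit paragraph directly govern only the interview and clinical examination. Clarification would be cheap: one sentence stating that the outcome tests apply to every group, and two names added to a list.

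Part of this stands. The wording is ambiguous, SF-36 is absent from a list that names its sister questionnaires, and tidying the paragraph would do no harm.

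What does not stand is the step from ambiguity to lost data. It requires that an examination plan not shown here omits an outcome test, and nothing in the protocol says that it does; referring to a separate approved plan is not a defect in itself. It also requires staff to work from one paragraph while ignoring the outcome list of the same short document. The clearer gap, SF-36, concerns the last-listed secondary outcome, whereas the weight of the argument comes from the primary outcome, for which strain echocardiography is named in both places. Writing the clarification in would only repeat what the outcome sections already require.

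**Conclusion.** No change follows. The visit paragraph is incomplete: one test-based outcome of 7 is clearly missing from its list, one is not clearly covered, and the sentence on group plans does not state that the outcome tests are common to all. The outcome sections close the gap by requiring all 7 at 3 and 12 months without limit by diagnosis, and nothing in the document contradicts them.

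This rests on two assumptions: that the study is run from the whole protocol, and that the approved group plans respect its outcome list. The protocol gives no reason to doubt either. Evidence that a group plan actually omits strain echocardiography or another outcome test at 12 months would change the conclusion, but the protocol contains none.

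### Does the protocol promise a prognostic analysis of blood vessel parameters that it never arranges to measure?

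*Protocol*

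**What the plan says.** The paragraph on the 3- and 12-month visits, which closes the Protocol, ends by stating that the incidence of MACCE will be assessed and that "the prognostic value of the structural and functional parameters of the myocardium and blood vessels will be assessed".

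The same paragraph describes what is done at the visits:

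- After interview, clinical examination and anthropometry: "measurement of temperature, heart rate, blood pressure, oxygen saturation, dyspnea, myalgia are performed".
- "Each patient undergoes electrocardiography, general and biochemical blood tests, microalbuminuria test".
- "Lungs CT, echocardiography with myocardial strain assessment, six-minute walk test", followed by "assessment of symptoms of stress, anxiety and depressive disorders (PSS-10 GAD7, PHQ9, respectively) are performed".

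It adds that the 12-month examination follows an approved plan by diagnosis group. That plan is not reproduced.

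The objective is "to evaluate the impact of COVID-19 pneumonia on transthoracic echocardiography and other myocardial parameters during 1 year follow-up", with a view to monitoring cardiovascular events and predicting outcomes. Under Design, "Patients undergo clinical, instrumental and laboratory diagnostics tests during follow-up visits at 3 and 12 month". Under Population, "The observation period was 12 months", with a window of 2 weeks either side.

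The outcome list has one primary outcome (echocardiographic cardiac function, global strain) and seven secondary outcomes. Item 6 is activated clotting time and item 7 is SF-36, both at 3 and 12 months.

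**The concern.** The closing sentence sets vessels beside the myocardium and says their structural and functional parameters will be assessed as predictors. A reader who looks for the vessel measurement finds none named. The outcome list has no vessel parameter, the objective speaks of myocardial parameters, and the visit paragraph mentions CT for the lungs and echocardiography with strain. Coronary artery disease and obliterating atherosclerosis appear only as diagnoses.

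Timing makes this look worse. Observation ends at 12 months, so a vessel value first taken at the 12-month visit precedes no observed event. Only a value from the 3-month visit can serve as a predictor, and a baseline missed there cannot be recovered. If no vessel value were recorded at 3 months, that part of the stated analysis could not be done for any of the 380 planned patients.

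A smaller point lies beside it. The visit paragraph names three questionnaires that correspond to no declared outcome (PSS-10, GAD7, PHQ9). It does not name SF-36 or activated clotting time, which are declared outcomes.

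**Working it through.** The Protocol gives no figure on this point to reproduce. The check is a count, a timeline and a comparison of the texts.

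**1. Items in the visit paragraph.** Clinical: interview, clinical examination, anthropometry, temperature, heart rate, blood pressure, oxygen saturation, dyspnea, myalgia = 9. ECG and laboratory: electrocardiography, general blood tests, biochemical blood tests, microalbuminuria = 4. Imaging, exercise and questionnaires: lung CT, echocardiography with strain, six-minute walk, PSS-10, GAD7, PHQ9 = 6. Total 9 + 4 + 6 = 19, a figure that depends on how one splits the items. Named measures of vessel structure: 0. Measures bearing directly on vessel function: 1 (blood pressure). Microalbuminuria bears on it indirectly.

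**2. Outcomes.** 1 primary + 7 secondary = 8. Vessel parameters among them: 0, since MACCE counts events.

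**3. Timeline.** Follow-up after the 3-month visit is 12 − 3 = 9 months. With 2 weeks' tolerance at each end the range is 9 months ± 4 weeks, or 9 ± 0.92, about 8.1 to 9.9 months. After the 12-month visit it is 12 − 12 = 0. The premise that only 3-month values can predict is therefore right.

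**4. Is the visit paragraph a complete list?** The declared outcomes can be used to test this:

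| Declared outcome | Named in the visit paragraph? |
|---|---|
| Strain echocardiography | yes |
| MACCE | yes |
| Lung CT | yes |
| Six-minute walk | yes |
| Creatinine clearance | no; falls under biochemical tests |
| C-reactive protein | no; falls under biochemical tests |
| Activated clotting time | no; could fall under laboratory tests in Design |
| SF-36 | no |

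Four of 8 are named and 4 are not, yet all 8 are study outcomes. The paragraph is a narrative summary, so its silence on a measurement does not show that the measurement is not made. Vessel values differ in one respect: the outcome list does not supply them either. That makes them unspecified, which is weaker than uncollected.

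**5. Could the scheduled tests supply a vessel value at 3 months?** Blood pressure does so directly for function. For structure, echocardiography and lung CT are both performed at 3 months and could yield vessel dimensions. The visit paragraph describes an echocardiogram with strain assessment added, the objective refers to transthoracic echocardiography in general, and the primary outcome is headed as cardiac function. None of these confines the examination to strain. CT is assigned to parenchymal damage as an outcome, but nothing forbids reading other values from the same scan.

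**6. What depends on the sentence?** It is neither an outcome nor part of the objective, and the hypothesis concerns the myocardium. No declared result changes with it.

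**The case for a change.** The strongest case for acting is that which examinations patients undergo is protocol content. An analysis plan can choose among recorded values, but it cannot create one that was never recorded at 3 months. The group examination plan does not help, because it is tied to the 12-month visit and to diagnosis groups. The reference to instrumental tests under Design is a heading with no vessel test under it. And unless someone says that vessel dimensions are to be read, nothing obliges the site to record them. Deleting three words would cost nothing.

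Much of this stands. No structural vessel parameter is named, the 12-month plan cannot supply a baseline, and the wording would be better if it said what is meant.

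What does not stand is the step from unnamed to absent. It requires treating the visit paragraph as exhaustive for vessels while accepting that it is not exhaustive for SF-36, clotting time, creatinine clearance and C-reactive protein. It also requires the strictest reading of a compressed phrase, namely that both structural and functional parameters are promised for both myocardium and vessels.

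Nor does any available change earn its place. Naming the parameters or their source is detail that the analysts supply. A new vessel test would mean an extra examination for 380 patients in support of a sentence outside the outcomes and the objective. Deleting the three words alters no result.

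**Conclusion.** No change is called for. The closing sentence is loosely worded: it mentions vessels without saying which parameter is meant. This is a gap that an analyst fills sensibly by drawing on values from tests already scheduled at 3 months: blood pressure for function, and any vessel dimensions available from the echocardiogram or CT for structure. A loss of vessel data in all 380 patients is not shown.

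This rests on two assumptions. The visit paragraph is a summary, which its omission of four declared outcomes supports. The scheduled imaging can yield a usable vessel dimension, which the Protocol neither states nor rules out. If the second failed, the loss would be confined to the structural vessel half of one sentence. The primary outcome, the seven secondary outcomes and the objective would be untouched.

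The absence of SF-36 and activated clotting time from the visit paragraph is clerical. Items 6 and 7 of the secondary outcomes fix both at 3 and 12 months, and no data are lost. Collecting three questionnaires that are not outcomes is not an error.
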